12.0 STATISTICAL CONSIDERATIONS

12.1 Data Analyses for the primary and secondary endpoints

We hypothesize that high risk subjects with precancerous gastric lesions will benefit from eflornithine, by reducing DNA damage, inflammation, and bacterial virulence, leading to attenuated histopathology and cancer risk. The primary objective is to assess whether eflornithine affects gastric epithelial cell DNA damage, measured at the 6 month time point, as assessed by percent positive cells in each patient, measured by IHC for gamma H2AX. We expect 150 patients in each group (eflornithine vs. placebo). We expect 100 patients in each *H. pylori* subgroup (*H. pylori* negative, *H. pylori* positive treated, *H. pylori* positive untreated [decline treatment]). We will examine the main effect of treatment and the effect modification from *H. pylori* status and treatment in a multivariate model.

We hypothesize a 50% reduction in DNA damage from baseline at the 6 and 18 months. We expect a modest reduction of eflornithine (10%) effect on DNA damage after treatment cessation (months 18-24), which nonetheless may remain statistically significant. We also expect a reduction in the histopathology score by 0.16-0.18 units at 18 months. We base these estimations on our prior published studies.[8,9] We assume a two-sided alpha of 0.05 and 80% power. For the main comparison, DFMO vs. placebo at 6 months (150 subjects each), a difference in DNA damage of $\geq 18\%$ (IHC for gamma H2AX) is hypothesized. A difference of ≥ 0.1 units in histopathology score at 18 months is expected.

Subgroup analysis (50 subjects each) at 6 months, where the comparator is *H. pylori* negative may detect a difference of $\geq 36\%$ and $\geq 31\%$ in DNA damage, respectively, and may detect at 18 months a difference of ≥ 0.15 units in histopathology score for both comparisons. These calculations assume normally distributed endpoints and use standard deviations from our prior work. The size of differences chosen for computations has been reduced to allow a 10% loss to follow up.

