Generalized linear models with a Gaussian link are used to analyze difference in means of DNA damage (flow cytometry, immunostaining), and histopathology at 18 months. The primary endpoint will be reported in terms of marginal means and their difference (DFMO/placebo) with 95% confidence intervals (95%CI) adjusted for baseline variables (age, gender, etc.) and baseline dependent variable values. Mixed models will be used to analyze secondary endpoints including the longitudinal changes from baseline to 6, 18, and 24 months. Time between measurements will be included in the model so that random slopes for the dependent variable at each point in time and random intercepts for each subject will be initially assumed. Adjusted marginal means and 95%CI will be reported with significance levels. The subgroup analysis will involve entering the subgroup analysis variable into generalized linear mixed models: Negative *H. pylori* status, *H. pylori* positive and treated, and *H. pylori* positive and refused treatment. Marginal means and 95%CI are reported for each subgroup after adjusting for baseline variables and including the main independent variable (treatment). A main effects model and an interaction model will be assessed for the treatment and subgroup variables. Prior experience with all three measurements has shown them to be normally distributed. Comparisons of AEs and SAEs between each of the treatment groups will also be performed using person-times poisson rates, with rates being reported using exact 95% confidence intervals. Lastly, we will examine the interaction of treatment arm and genotype expression with respect to different outcomes. STATA 13 is used for computations.

12.2 Accrual Monitoring. The historical experience for patient recruitment is approximately 150 patients per year. The estimated 10% dropout rate is based on prior studies, with excellent 1-year follow-up of >93% at these same study sites.[59,60] The general populations are keenly aware of the impact of gastric cancer in their regions, and the need for prevention. We anticipate balanced recruitment between the two study sites, 150 subjects per site, but with a flexible recruitment strategy. The enrollment at each individual site will be capped at 240 (80%).

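### Does reducing the planned differences to allow for 10% loss to follow-up leave the primary comparison below 80% power?

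*Combined protocol and SAP*

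**What the plan says.** Section 12.1 of the combined protocol and SAP sets the operating characteristics: "We assume a two-sided alpha of 0.05 and 80% power". The main comparison is described as "For the main comparison, DFMO vs. placebo at 6 months (150 subjects each"), and for it "a difference in DNA damage of $\geq 18\%$ (IHC for gamma H2AX) is hypothesized". Two sentences cover how the figures were obtained: "These calculations assume normally distributed endpoints and use standard deviations from our prior work", and "The size of differences chosen for computations has been reduced to allow a 10% loss to follow up". No SD, unreduced difference or reduction factor is printed.

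The same section states larger expected effects. It hypothesises a 50% fall in DNA damage from baseline at 6 and 18 months, and expects a histopathology reduction of 0.16 to 0.18 units at 18 months. The figures attached to sample sizes are smaller: 18% and 0.1 units for the main comparison; 36%, 31% and 0.15 units for subgroups of 50.

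Section 12.2 gives the source of the loss rate: "The estimated 10% dropout rate is based on prior studies, with excellent 1-year follow-up of >93% at these same study sites".

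**The concern.** With N, SD, alpha and power fixed, losing 10% of patients makes the smallest detectable difference larger, by a factor of 1/√0.9 = 1.054. A sentence saying that differences were *reduced* to allow for loss therefore looks like an adjustment in the wrong direction. The 18% also stands beside 150 per arm rather than 135, as if loss had been left out.

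The scale raises a second doubt. The primary objective estimates a mean difference in percent-positive cells, which runs from 0 to 100. Taken as percentage points, 18 at 80% power implies an SD above 50, which such a variable cannot have.

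If both points held, the primary power statement would promise something the design does not deliver under its own loss assumption, and it could not be tied to the endpoint.

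**Working it through.** **Inputs.** Two-sided alpha 0.05, 80% power, 150 per arm, 18%, 50 per subgroup cell, 0.1 and 0.15 units, expected 0.16 to 0.18 units (all section 12.1); 10% loss (sections 12.1 and 12.2). This gives 135 per arm and 45 per cell. The SD is not stated.

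**Formulas.** Two-sample normal approximation, with 1.960 + 0.842 = 2.8016:

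- 80%-power difference = 2.8016 × SD × √(2/n)
- power = Φ(d / (SD × √(2/n)) − 1.96)

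**1. The plan's figure.** Without an SD, 18% cannot be reproduced independently. The SD can only be solved backwards: 18 / (2.8016 × √(2/150)) = 55.6 if 18% belongs to 150 per arm, or 18 / (2.8016 × √(2/135)) = 52.8 if it belongs to 135. The subgroup figure does not settle which: 18 × √(150/50) = 31.2, close to the stated 31%, but 135 and 45 give the same ratio.

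**2. What each reading implies.**

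| Reading of the 18% | Consequence at 135 per arm |
|---|---|
| Unadjusted 80%-power difference at 150 | 75.7% power for 18%; 80%-power difference 18.97% |
| Already computed on 135 evaluable | 80.0% power (84.0% at 150) |
| Assumed effect, made smaller before the calculation | At least 80% power for any unreduced effect of 18.97% or more |
| Detectable difference literally lowered from 18.97% or 20% | 71.3% or 66.7% power for 18% |

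**3. Why the third reading covers the loss.** If N gives 80% power for a reduced effect k × D, power for D itself at 0.9N is Φ(2.8016 × √0.9 / k − 1.96). This is at least 80% whenever k is at most √0.9 = 0.949, that is, D ≥ 18 / 0.949 = 18.97%. With k = 0.9 (D = 20%, an illustration that is not in the documents) it is Φ(2.953 − 1.96) = 84.0%. Making the assumed effect smaller is then in the right direction.

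**4. Does the plan's own text fit that reading?** The quoted sentence speaks of differences chosen for the computations, and the 18% is called hypothesised. The histopathology figures allow a numerical check:

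- The expected 0.16 to 0.18 units cut by 10% give 0.144 to 0.162, which brackets the subgroup figure of 0.15.
- If 0.15 has 80% power at 50 per cell, SD = 0.15 / (2.8016 × √(2/50)) = 0.268. At 45 per cell the standard error is 0.268 × √(2/45) = 0.0564. Power for 0.16 is Φ(2.835 − 1.96) = 81%; for 0.18 it is Φ(3.189 − 1.96) = 89%.
- If 0.1 has 80% power at 150 per arm, SD = 0.309. At 135 the standard error is 0.309 × √(2/135) = 0.0376, and power for 0.16 is Φ(4.25 − 1.96) = 99%.

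The two histopathology SDs (0.309 and 0.268) need not conflict: 0.15 × √(50/150) = 0.087, which rounds to 0.1.

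**5. The scale.** Suppose 18 does mean percentage points. The SD of a 0–100 variable is at most 50, and adjustment for baseline cannot raise it. At 135 per arm, power is at least Φ(18 / (50 × √(2/135)) − 1.96) = Φ(2.958 − 1.96) = 84%. On that scale the shortfall is impossible. If 18% is instead relative to a mean, the implied SD is 55.6% of that mean and breaks no bound.

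**The case for a change.** The strongest counter-argument is that the subgroup sentence speaks of what the comparisons may detect. For a detectable difference, *reduced* is the wrong direction. Moreover, if a larger assumed effect was cut to 18%, power for 18% itself at 135 is still 75.7%; the protection applies only to an unreduced effect that the plan never states. The one reading that gives 18% exactly 80% power at 135 has the difference raised from about 17.1%, which does not match the verb.

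This is correct as far as it goes. But when an assumed effect is deliberately made smaller, the effect to be protected is the larger one, and the section does state larger expectations. They are not a perfect match: the 50% is a fall from baseline, while the 18% compares arms. The histopathology agreement is therefore the better evidence, and it is suggestive rather than conclusive.

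The 75.7% also depends on details the plan does not give. Rounding of the 18% alone (17.5 to 18.49) moves it between 78.0% and 73.5%. A loss of 7%, in line with the follow-up cited in section 12.2, gives 77.1%. The formula ignores the planned adjustment for baseline values; if the SDs are unadjusted, a baseline correlation of √0.1 = 0.32 recovers a 10% loss.

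What stands is that the sentence is terse, and that the SD, the scale of the 18% and the unreduced difference are not printed. The unadjusted reading cannot be ruled out.

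**Conclusion.** The concern does not hold. The figures of 75.7% and 18.97% are arithmetically right, but only if 18% is an unadjusted 80%-power difference at 150 per arm. The plan does not say so, and it states that an allowance for loss has already been made. A reduction of the assumed effect before the calculation is a legitimate, conservative allowance. It fits the wording and the histopathology figures, and it keeps at least 80% power at 135 for any unreduced effect of 18.97% or more. The scale argument does not support the concern either: in percentage points, power at 135 is at least 84%.

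Even on the least favourable of the ordinary readings, the unadjusted one, the gap is about 4 points of power and 1 point of difference. What a null result excludes will be read from the 95% confidence interval for the adjusted mean difference, which section 12.1 requires, not from planned power. Restated values of 19.0% and 0.105 cannot be derived from the documents, and they would count the loss twice if 18% already rests on 135.

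This conclusion assumes the normal approximation, 10% loss in both arms, and the reading of the sentence as a reduced assumed effect. The missing SD, scale and unreduced difference are reporting detail; their absence does not show the design to be underpowered.

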1.0 OBJECTIVES

Overview of Study Design

This is a clinical study of the efficacy of oral alpha-difluoromethylornithine (eflornithine or DFMO) in male and female subjects ages 30-69 with gastric premalignant lesions in high risk regions of Latin America. The primary intervention is the randomized, double-blind assignment of patients to once daily eflornithine (500 mg) versus placebo for an 18 month treatment period. The primary endpoint is gastric epithelial cell DNA damage, measured at the 6 month time point, assessed by percent positive cells in each patient, measured by gamma H2AX immunohistochemistry (IHC). Gastric precancerous lesions are defined as chronic atrophic gastritis (CAG) and intestinal metaplasia (IM). Patients will be clinically assessed with endoscopy and gastric biopsy at four time points: 0, 6, 18, and 24 months the assessments at 0 and 24 months are considered part of usual clinical care in subjects with precancerous lesions in high risk regions. Overall, the efficacy of eflornithine is assessed by its effect on: 1) DNA damage, 2) histology scoring, and 3) gastric polyamine levels.

Primary Objective

1.1 The difference in cell DNA damage between patients treated with DFMO and patients treated with placebo at 6 months. The cell DNA damage is measured using the percent positive gastric epithelial cells assessed by IHC for gamma H2AX. The mean difference between the two groups at 6 months will be calculated, accounting for their baseline measurements.

Secondary Objectives

1.2 The difference in cell DNA damage between patients treated with DFMO and patients treated with placebo for 18 months, and then followed for an additional 6 months. The cell DNA damage is measured using the percent positive gastric epithelial cells assessed by IHC for gamma H2AX. The mean difference between the two groups at 18 and 24 months will be calculated, accounting for their baseline measurements.

1.3 The differences in the gastritis histopathology score between patients treated with DFMO and patients treated with placebo for a total of 18 months, and followed for an additional 6 months. The gastritis histopathology score is measured with a quantitative scale 0.0-6.0, for atrophy, intestinal metaplasia, and dysplasia. The mean differences between the two groups at 6, 18, and 24 months will be calculated using mixed models, accounting for their baseline measurements.

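### The secondary mixed model is described by elapsed time and random slopes with no treatment-by-visit term, so it does not secure the arm differences at 6, 18 and 24 months that the objectives require

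*Combined protocol and SAP*

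**What the plan says.** Section 12.1 assigns the secondary endpoints to mixed models: "Mixed models will be used to analyze secondary endpoints including the longitudinal changes from baseline to 6, 18, and 24 months". On time it says "Time between measurements will be included in the model so that random slopes for the dependent variable at each point in time", and it adds that "random intercepts for each subject will be initially assumed". No rule is given for moving away from that starting structure. The only interactions named in 12.1 are treatment with *H. pylori* subgroup and treatment arm with genotype.

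The targets are visit-specific. For DNA damage, objective 1.2 (repeated in 11.2) states: "The mean difference between the two groups at 18 and 24 months will be calculated, accounting for their baseline measurements". Objective 1.3 (repeated in 11.3) asks for histopathology differences at 6, 18 and 24 months and names mixed models as the tool. Under Section 8.2 drug is given to Month 18, and Month 24 is off drug.

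Section 12.1 also gives the profile the investigators expect for DNA damage: "We hypothesize a 50% reduction in DNA damage from baseline at the 6 and 18 months", followed by "We expect a modest reduction of eflornithine (10%) effect on DNA damage after treatment cessation" between Months 18 and 24.

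A separate model appears in the same section: "Generalized linear models with a Gaussian link are used to analyze difference in means of DNA damage (flow cytometry, immunostaining), and histopathology at 18 months". From it follows the primary endpoint, reported as marginal means "adjusted for baseline variables (age, gender, etc.) and baseline dependent variable values".

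**The concern.** Elapsed time with a slope per subject is the usual language of a continuous-time trajectory. The expected profile is a fall by Month 6, a plateau to Month 18, and some loss of effect after the drug stops. A straight line from baseline cannot follow that shape. A model with no treatment-by-time term cannot show any change in effect at all.

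At stake is whether the effect persists six months off drug. The contrast between Months 18 and 24 answers that question, and Month 24 is a visit that Section 12.1 assigns only to the mixed model. The *H. pylori* subgroup models in 12.1 are also mixed models and would inherit the time coding. In one of those subgroups, expected to number about 100 of 300 (7.2), eradication treatment is given at Month 6 (7.3), which is a second possible break in the trajectory.

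**Working it through.** **The plan's own figure.** The plan gives no figure for the mixed model. Its between-arm figure for DNA damage is at least 18% at 6 months, with 150 per arm, two-sided alpha 0.05 and 80% power. The SD is not stated, so the figure can only be inverted: SD = 18 / [(1.960 + 0.842) × √(2/150)] = 55.6. With that SD and 50 per group, the detectable difference is 2.802 × 55.6 × √(2/50) = 31.2, close to one of the two subgroup figures (31%). This is a consistency check and does not bear on the time coding.

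**Inputs.** Visits are at 0, 6, 18 and 24 months (8.3). The illustrative between-arm effect, written as a reduction, is 50 at 6 months, 50 at 18 and 45 at 24, reading the 10% loss as relative. If it means percentage points, Month 24 is 40. Treating 50 as a between-arm effect is an assumption, because 12.1 states it as a change from baseline.

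**Model examined.** Linear time, treatment and treatment-by-time, with random intercept and slope. With balanced complete data the expected arm difference for codings A and C below equals the ordinary least-squares line through the true differences, so no variance assumption is needed.

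**Coding A: baseline as an outcome row, arms free at baseline.** Mean time = 12; mean effect = 145/4 = 36.25; Sxx = 144 + 36 + 36 + 144 = 360; Sxy = −6×50 + 6×50 + 12×45 = 540. Slope = 540/360 = 1.5 per month; intercept = 36.25 − 12×1.5 = 18.25. Fitted: 27.25, 45.25, 54.25. Month 6 is low by 22.75, Month 18 is low by 4.75, Month 24 is high by 9.25, and a spurious difference of 18.25 appears at Month 0.

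**Coding B: baseline as an outcome row, arms constrained equal at baseline.** The difference is a line through the origin, so it is largest at Month 24 by construction. Over four assumed sets of intercept, slope and residual SDs, (0, 0, 1), (35, 0.5, 40), (40, 1, 35) and (20, 1, 50), the fits run from 10.9 to 14.6 at Month 6, 32.6 to 43.8 at Month 18 and 43.5 to 58.5 at Month 24.

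**Coding C: baseline as a covariate, post-baseline visits only.** Mean time = 16; mean effect = 48.33; Sxx = 100 + 4 + 64 = 168; Sxy = −10×50 + 2×50 + 8×45 = −40. Slope = −0.238. Fitted: 50.7, 47.9, 46.4. The errors are +0.7, −2.1 and +1.4, and the effect is smallest at Month 24.

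**Other profiles, same formulas:**

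| True effect at 6/18/24 | Coding A | Coding C |
|---|---|---|
| 50/50/45 | 27.25/45.25/54.25 | 50.7/47.9/46.4 |
| 50/50/40 | 27/43/51 | 51.4/45.7/42.9 |
| 50/50/25 | 26.2/36.2/41.2 | 53.6/39.3/32.1 |
| 50/50/0 | 25/25/25 | 57.1/28.6/14.3 |
| 18/18/16.2 | 9.8/16.3/19.5 | 18.3/17.2/16.7 |

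**No treatment-by-time term.** With equal weights on the three post-baseline visits, one effect is reported throughout: (50 + 50 + 45)/3 = 48.3, or 33.3 for 50/50/0.

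**A random effect at every visit, read literally.** With one value per subject per visit, it cannot be separated from residual error.

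**Categorical visit with treatment-by-visit.** The expected estimates equal the true profile in every row of the table.

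**The case against.** Linear time is an inference. Section 12.1 says neither linear, continuous nor categorical, its wording about each point in time can be read as visit-specific, and the structure is only a starting assumption. The objectives define their targets by visit, and 12.1 promises adjusted marginal means. All of this stands: the finding is that the coding is open and that its natural reading is unsuitable, not that a straight line has been prescribed.

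A reader might infer that the model will report its largest effect after the drug has stopped. The documents do not support that as a general claim. It happens under codings A and B for the hypothesised profile. Coding C fits the objectives' wording about accounting for baseline at least as well, and there the errors are about 2 points and nothing is reversed. That close fit, however, relies on the off-drug loss being small, which is what Month 24 is there to test. With full loss, coding C understates Month 18 by 21 points and shows 14 points of effect where none remains.

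Three further objections also stand:

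- A reader might blame the random slopes. The bias comes from the fixed-effect shape of time, and random slopes are compatible with categorical visit means.
- A reader might extend the point to the primary result. That 6-month DNA-damage comparison is a separate baseline-adjusted GLM and is not touched.
- The 50 is a within-arm change. On the plan's 18% between-arm scale the absolute errors shrink in proportion, although coding A still recovers only 9.8/18 = 54% of the Month 6 effect.

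**Conclusion.** The concern holds as a gap in specification with a real consequence for the secondary analyses. As written, Section 12.1 does not guarantee the visit-specific contrasts in objectives 1.2 and 1.3. If time is linear, the illustrative Month 6 estimate is 27 or 51 depending only on whether baseline is an outcome row (coding A) or a covariate, and the Month 24 estimate is 54 or 46 against a true 45. That choice could be made after the data are seen.

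These sizes assume complete balanced data, a linear treatment-by-time term that 12.1 does not name, and the 50% figure used as a between-arm effect. For histopathology the plan gives no time profile, only expected values at 18 months, so the bias there cannot be sized. The Month 6 part of the point matters mainly for histopathology, since DNA damage at 6 months belongs to the primary analysis.

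**What to change.** In Section 12.1, replace the sentence on time and random slopes with a repeated-measures specification:

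- visit as a categorical factor (6, 18, 24 months), treatment, and treatment-by-visit;
- the baseline value as a covariate, with baseline-by-visit;
- a pre-specified within-subject covariance, for example unstructured, fitted by REML;
- the treatment contrast with its 95% CI reported at each visit.

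Use the same time coding in the *H. pylori* subgroup mixed models. State which model is reported for histopathology at 18 months, since 11.3 assigns it to the mixed model and 12.1 also lists it under the GLM. Other covariance structures, or a constrained common baseline with categorical visit, would also be acceptable if fixed in advance.

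The cost is wording, a few extra parameters, and slightly wider intervals than a straight-line model, all minor with about 300 patients. Categorical visits also ignore where in the endoscopy window (−30/+60 days, 8.3) a biopsy falls. If that matters, a model in actual elapsed time can be kept as a sensitivity analysis. If the sponsor already intends categorical visits, one sentence settles the point.

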7.0 STRATIFICATION FACTORS

Patients will be randomized to one of two treatment groups: eflornithine versus eflornithine placebo, with 150 subjects in each treatment group. A dynamic balancing algorithm will be used for randomization, with stratification by study site. *H. pylori* status is integrated into the analysis, but stratification is not performed by *H. pylori* status.

7.1 Study sites. Study enrollment will be competitive across up to three participating sites. The enrollment at each individual site will be targeted at 240 (80%), with the exception of extenuating circumstances (e.g., natural disaster, recruitment limitations, etc.).

7.2 *H. pylori* subgroups. Three subgroups of subjects with precancerous lesions will be studied as a secondary analysis, based on *H. pylori* status and acceptance of eradication treatment at enrollment: 1) *H. pylori* negative; 2) *H. pylori* positive, decline antibiotic treatment (50%); and 3) *H. pylori* positive, accept antibiotic treatment (50%). Historically, given the high prevalence of *H. pylori* infection and the natural history of reinfection, about 50% of subjects decline or accept antibiotic eradication, respectively. Thus, these 3 subgroups are common clinically we expect a *balanced distribution* at our study sites (see study schema). In summary, we expect 150 subjects in each treatment group (eflornithine, placebo) and 100 subjects enrolled in each *H. pylori* subgroup.

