7.3 *H. pylori* eradication. The secondary intervention is *H. pylori* treatment of subjects of the subgroup who are *H. pylori* positive and desire treatment, per usual standard of care. Subjects are treated with standard triple therapy (clarithromycin 500 mg, amoxicillin 1000 mg, lansoprazole 30 mg) twice daily for 14 days. This is the optimal regimen in Latin America, based on RCT results.[59] Patients are permitted to choose alternative *H. pylori* eradication regimen, per usual standard of care, in consultation with the site investigator. Patients will be treated at the 6 month time point. This *H. pylori* eradication treatment timing permits the maximum number of study subjects on DFMO monotherapy for the 6 month primary endpoint. This timing is ethical given the lifelong infection with *H. pylori* in >80% of our populations, the natural history of reinfection, and the limited short term benefit of *H. pylori* eradication for subjects with premalignant lesions. Subjects who elect to change their decision on *H. pylori* treatment during the initial 6 month period are permitted to do so. In addition, we expect infection recurrence rates of 8% in Honduras at the 18 month point based upon our Latin America RCT. If infected at 24 months, subjects will be offered treatment per local standards of care and outside of this protocol. [59,60]

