The endoscopy with standard biopsies of the gastric mucosa will be done at four time points: Months 0 (pre-study), 6, 18, and 24. Patients are screened at the time of the index endoscopy, previously scheduled for clinical indications per local standard of care. Samples obtained at the time of the index endoscopy performed per standard of care prior to informed consent for this study may be submitted for research once informed consent is obtained. The Month 0 (pre-study) and Month 24 endoscopies are part of usual care clinical screening and surveillance endoscopies in high risk regions, per local and emerging international standards.[61] The allowable timeframe for each endoscopy is - 30/+60 days. The gastric mapping biopsy protocol for histology follows the international protocols,[61] and with additional research biopsies per longstanding protocol. (Appendix 16.2).

Biopsy mapping of the gastric mucosa for histopathology is part of usual care of patients at study sites, and adherent to emerging international standards for stomach precancerous lesions. Five formalin-fixed biopsies are obtained from the antrum (2), corpus (2), and incisura (1). Two sets of research small pinch biopsies are obtained for the study, preserved for study analyses.

The potential risks of endoscopy include perforation, bleeding, infection, and drug reaction. Biopsies of the stomach are considered a routine component of diagnostic upper endoscopy. The serious adverse event rate for upper endoscopy with biopsies is less than 1/6000 cases (<0.02%).[62] Perforation and bleeding may require a repeat endoscopy, and in some cases, surgery. Infection at the biopsy sites is highly unlikely. Allergic reactions to medications used for procedure sedation are extremely uncommon, and would be treated immediately if they should occur.

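### The longitudinal H. pylori subgroup models name no subgroup-by-visit term, so fitted as written they average visits before and after the Month 6 eradication

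*Combined protocol and SAP*

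**What the plan says.** - **Model (12.1).** Secondary endpoints are analysed with mixed models over the changes from baseline to Months 6, 18 and 24. For the H. pylori groups, "The subgroup analysis will involve entering the subgroup analysis variable into generalized linear mixed models", with three levels: negative, positive and treated, positive and refused. Then "A main effects model and an interaction model will be assessed for the treatment and subgroup variables". For output, "Marginal means and 95%CI are reported for each subgroup"; no visit is given.
- **Time (12.1).** "Time between measurements will be included in the model so that random slopes for the dependent variable at each point in time" and random intercepts are assumed initially. No variances or correlations are stated.
- **Groups (7.2).** They rest on H. pylori status and "acceptance of eradication treatment at enrollment", which is the patient's own choice.
- **Eradication (7.3).** "Patients will be treated at the 6 month time point", so that as many patients as possible are on DFMO alone for the primary endpoint. Patients may change their decision during the first six months.
- **Measurement (8.3).** "The endoscopy with standard biopsies of the gastric mucosa will be done at four time points: Months 0 (pre-study), 6, 18, and 24".
- **Drug exposure (8.2).** Dosing lasts 18 months, and Month 24 falls six months after it ends. Section 12.1 expects the DFMO effect on DNA damage to be reduced by 10% over that interval.

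**The concern.** In the longitudinal models the label positive and treated covers two different states. At Month 6 these patients are, by design, still untreated positives like the refusers; at Months 18 and 24 they have been treated. A single subgroup coefficient cannot represent both. Having time in the model does not help: a time effect or random slope common to all groups allows no shift specific to the treated group.

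Section 12.1 names effect modification by H. pylori status and treatment as something the trial will examine. If the models are fitted as listed, the answer describes a mixture of visits, and a real difference between treated and refused patients is harder to see. If visit terms are added only once data are in hand, the choice is open to the charge of being driven by the results.

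**Working it through.** **1. The plan's own figures.** The documents state no eradication effect, no DFMO-by-eradication effect and no treated-versus-refused contrast. The nearest figures are subgroup detectable differences with 50 patients each: at least 36% and 31% in DNA damage at Month 6, and at least 0.15 units in histopathology score at Month 18, with H. pylori negative as comparator. Scaling the main comparison gives 18% × √(150/50) = 31.2%, in line with 31%; 36% needs a standard deviation 36/31.2 = 1.15 times as large. Without the standard deviations the figures can be neither confirmed nor refuted. They are single-visit figures and do not describe the pooled models.

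**2. Exposure at each follow-up visit (7.3, 8.2, 8.3).**

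| Visit | Eradication in the treated group | DFMO in the active arm |
|---|---|---|
| Month 6 | not yet | on |
| Month 18 | done | on (end of dosing) |
| Month 24 | done | off for 6 months |

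**3. Treated versus refused.** Let the true contrast be 0 at Month 6 and d at Months 18 and 24. A visit-constant term estimates (1 − w)d, where w is the weight on Month 6:

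w = (v_L − c) / (v_6 + v_L − 2c)

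Here v_6 is the Month 6 variance, v_L the variance of the mean of Months 18 and 24, and c their covariance.

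- Equal variances and common correlation ρ: v_6 = 1, v_L = (1 + ρ)/2, c = ρ. Then w = [(1 − ρ)/2] / [3(1 − ρ)/2] = 1/3 for any ρ. The estimate is 0.67d.
- Baseline also a response: two of four equally weighted visits precede eradication, so the estimate is 0.50d.

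**4. Other covariances (all assumed), three follow-up visits.** General weights are V⁻¹1 / (1′V⁻¹1).

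| Assumption | Dilution |
|---|---|
| Month 6 SD 1.25 times later SD, ρ = 0.3 | w = (0.65 − 0.375)/(1.5625 + 0.65 − 0.75) = 19% |
| Same, ρ = 0.5 | 12% |
| Month 6 SD 1.5 times later SD, ρ = 0.5 | 0% |
| Random slope SD 0.02 per month, intercept variance 2, intercept–slope correlation −0.5 | 26% |
| Random slope SD 0.02 per month, correlation 0 | 39% |
| Autoregressive, 0.8 / 0.9 / 0.95 per month | 38% / 42% / 45% |
| Random slope SD 0.05 per month, correlation 0 | 61% |

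The random-slope rows take residual variance 1. Steeper slopes with positive intercept–slope correlation push the dilution past 100%, which reverses the sign.

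**5. Treated versus negative.** Let infected minus negative be D at Month 6, and let eradication remove a share s of it. The later contrast is (1 − s)D, but the equal-weight average is [D + 2(1 − s)D]/3. For s = 100%, 90%, 80% the later contrast is 0, 0.10D, 0.20D and the average is 0.33D, 0.40D, 0.47D. The averaged contrast is too large, not too small.

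**6. Treatment by subgroup.** Let the DFMO-by-eradication effect be 0 at Month 6, δ at Month 18 and fδ at Month 24. The equal-weight average is (0 + 1 + f)δ/3. If it fades in line with the plan's 10% (f = 0.9), this is 0.63δ; if nothing remains off drug (f = 0), it is 0.33δ.

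**7. Precision, illustration only.** With equal variances, the signal-to-noise ratio of the three-visit average relative to the mean of Months 18 and 24 is (2/3)√[3(1 + ρ) / (2(1 + 2ρ))] = 0.736, 0.707, 0.687 for ρ = 0.3, 0.5, 0.7. A contrast that had 80% power (z = 2.80) would then have 54%, 51% and 49%.

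**The case against.** The strongest reply is that the plan never says the subgroup effect is constant. Section 12.1 does not exclude visit terms. Sections 11.2 and 11.3 ask for arm differences by visit, and the subgroup power statement is itself tied to Month 6 and Month 18. A careful analyst might add the missing terms unprompted. This stands as far as intent goes: a reader might infer that a constant effect is prescribed, and the text does not support that. What remains is that the only models named for this variable are main effects and treatment by subgroup, in the one analysis where visit changes what the label means.

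Four further inferences should be resisted.

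- **That the loss is at least a third.** One third is the equal-weight case; step 4 shows both smaller and larger values.
- **That power falls to about half.** Step 7 presumes 80% power for a contrast to which the plan assigns no effect size or power.
- **That effects are always under-estimated.** This applies to treated versus refused. The comparator named in 12.1 is H. pylori negative, and there the error goes the other way.
- **That this is the trial's only route to the question.** Section 12.1 also plans an 18-month histopathology analysis, which contains no pre-eradication visit.

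**Conclusion.** The concern holds as a gap in the specification of a secondary analysis. Fitted as listed, the longitudinal subgroup models pool a pre-eradication visit with post-eradication visits. Treated versus refused is diluted by one third with equally weighted follow-up visits and by one half if baseline is a response; under other assumed covariances the loss runs from none to more than the whole effect. These sizes assume no eradication effect at Month 6 and the same effect at Months 18 and 24. They also assume that eradication is given after the Month 6 biopsy, which is the design's intent, although 7.3 lets patients change their decision earlier. Treated versus negative is pulled toward the infected state. The treatment-by-subgroup term mixes three conditions, one of them off drug.

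The Month 6 primary comparison and any single-visit 18-month analysis are untouched. Correcting the visit structure does not turn treated versus refused into a clean eradication effect, because acceptance is self-selected.

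**What to change.** In 12.1:

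- Enter visit as a category and add subgroup-by-visit and treatment-by-subgroup-by-visit terms, with treatment-by-visit alongside.
- Report subgroup means, and DFMO-minus-placebo differences by subgroup, separately at Months 6, 18 and 24.
- Take the on-drug DFMO-by-eradication contrast from Month 18 and report Month 24 separately as post-treatment. A single eradication indicator coded 0, 1, 1 is not equivalent for this contrast, since it forces a common effect on an on-drug and an off-drug visit.
- Describe treated-versus-refused contrasts as non-randomised.

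Cost: wording and no new data. With three follow-up visits the added terms number (3 − 1)(3 − 1) = 4 for subgroup by visit, 4 for the three-way term and 2 for treatment by visit, in about 300 patients. Per-visit intervals are wider than for a three-visit average by a factor √[3/(1 + 2ρ)] under equal variances: 1.37, 1.22 and 1.12 for ρ = 0.3, 0.5 and 0.7. That is the price of an estimate that refers to a defined exposure.
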